10.5.1.2 Sensitivity Analyses of Primary Efficacy Endpoints

To evaluate the robustness of the analysis results, sensitivity analyses will be performed as follows:

- The primary analysis will be repeated using the CAS.
- Non-parametric analyses (Quade test).
- **To evaluate the impact of missing data,**
 - A sensitivity analysis under the assumption that subjects that discontinued IP and have missing endpoint data have a mean zero percent change from baseline will be conducted using multiple imputation.
 - **If there are at least 25 subjects who discontinue IP but have non-missing week 24 endpoint data, the primary analysis model will be repeated using FAS with missing values imputed for subjects who discontinued IP. Missing values will be imputed using non-missing data from subjects who discontinued IP within the same treatment group.**

If there is notable number of subjects randomized but did not receive IP, ad hoc analysis (e.g. repeating primary analysis using all randomized subjects) may be performed.

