Procedures: Subjects being considered for participation in this study, and who have signed informed consent or subject assent, will be assessed for inclusion and exclusion criteria. Medical and medication history will be obtained. Subjects will undergo screening assessments, including a SC administration of placebo to evaluate tolerability of the SC injection via the prefilled AI/pen. Lipid eligibility screening must be conducted after the subject has been on a low-fat diet and receiving lipid lowering therapy that includes an optimal dose of a statin not requiring uptitration in the opinion of the investigator and has been stable for ≥ 4 weeks. Subjects should maintain their diet, lipid-lowering therapy, and exercise regimen unchanged throughout screening and all phases of study participation. Eligible subjects will be randomized to receive IP (evolocumab or placebo), in addition to their background lipid lowering therapy. An interactive voice response system and/or interactive web response system (IVRS/IWRS) will allocate subjects to administration of investigational product. Day 1 is defined as the day of first administration of investigational product. Subsequent study visits are at weeks 4, 12, 20, 22, and 24 (EOS, end-of-study). Day 1 and week 24 visits must be scheduled at approximately the same time of day, and should be performed as close as possible to 8 am as the hormones measured have diurnal variation. IP administration is every 4 weeks. Administration at weeks 8 and 16 can be at

the study site (optional visit) or at a location other than the study site. Last administration of IP is at week 20. Subjects who discontinue IP early for any reason will be asked to continue to return for all other study procedures and measurements until the end of the study.

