6.2.2 Dosage Adjustments, Delays, Rules for Withholding or Restarting, Permanent Discontinuation

There will be no dose adjustments in this study. If, in the opinion of the investigator, a subject is unable to tolerate a specific dose of IP, that subject will discontinue IP but will continue to return for all other study procedures and measurements until the end of the study.

If a subject is late for administration of IP, administration should occur as soon as possible. A full QM dose of IP should not be administered within less than 7 days of a previous dose. If a subject arrives for a visit with IP administration and IP was administered within the prior 7 days, the dose should not be administered but all other study procedures should be conducted. Administration of IP should occur as soon as possible but at least 7 days after the previous administration.

Subjects who completely miss a dose of IP will continue in the study and receive the next dose of IP per their schedule of administration.

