12.4 Investigator Responsibilities for Data Collection

The investigator is responsible for complying with the requirements for all assessments and data collection (including subjects not receiving protocol-required therapies) as stipulated in the protocol for each subject in the study. For subjects who withdraw prior to completion of all protocol-required visits and are unable or unwilling to continue the Schedule of Assessments ([Table 1](#)), the investigator can search publically available records [where permitted]) to ascertain survival status. This ensures that the data set(s) produced as an outcome of the study is/are as comprehensive as possible.

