3.2 Sample Size

This study is to provide clinical experience with evolocumab in approximately 150 pediatric subjects, compared to the current experience described in the Protocol [Sections 2.3](#) and [Section 2.4](#). Based on the treatment effect from the global phase 3 study in adult subjects with HeFH, evolocumab reduced LDL-C by approximately 55%. A planned total sample size of 150 pediatric subjects (100 randomized to evolocumab 420 mg QM and 50 randomized to placebo QM) will provide approximately 99% power in testing the superiority of evolocumab 420 mg QM over placebo. The sample size calculation is performed using a two-sided t-test with a 0.05 significance level, assuming a treatment effect of 40% reduction in LDL-C, a common standard deviation (SD) of 20%, and 20% of subjects discontinuing investigational product prior to completion of the study.

The power calculation is derived using nQuery version 7.01.

4. Study Endpoints and Covariates

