10.5.1 Analyses of Primary Endpoints

10.5.1.1 Primary Analysis of Primary Efficacy Endpoints

The estimand of primary interest is the difference in mean percent change from baseline in LDL-C at week 24 regardless of treatment adherence for subjects in FAS. A repeated measures linear effects model (Littell et al, 2000) will be used to compare the efficacy of evolocumab with placebo. The repeated measures model will include terms for treatment group, stratification factors (as appropriate), scheduled visit and the interaction of treatment with scheduled visit. To account for the repeated LDL-C measurements within a subject across the visits, the repeated measures linear effects model will use an unstructured covariance. Missing values will not be imputed when the repeated measures linear effects model is used. The analysis will use LDL-C values measured regardless of treatment adherence.

Multiplicity adjustment procedures are defined in [Section 10.1](#).

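### Does the pooled trigger of 25 retrieved discontinuers need to become a per-arm rule?

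*SAP*

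**What the plan says.** SAP 10.5.1.1 defines the primary estimand without regard to adherence: "The analysis will use LDL-C values measured regardless of treatment adherence". Nothing is imputed in that model.

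SAP 10.5.1.2 then lists two analyses for missing data.

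- The first has no trigger. It uses multiple imputation and assumes that "subjects that discontinued IP and have missing endpoint data have a mean zero percent change from baseline".
- The second is conditional: "If there are at least 25 subjects who discontinue IP but have non-missing week 24 endpoint data", the primary model is repeated on the full analysis set with imputation for IP discontinuers. The donor rule is "Missing values will be imputed using non-missing data from subjects who discontinued IP within the same treatment group".

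The SAP gives no reason for 25, no minimum by arm, and no instruction for this analysis below 25. SAP 9.3.2 only refers back to section 10.5.1, and Protocol 10.5.2 does not contain the second analysis. The SAP's summary of changes says that detail was added to this imputation, with FDA feedback as the rationale.

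The sample size section (SAP 3.2) assumes 100 evolocumab and 50 placebo subjects, with "20% of subjects discontinuing investigational product prior to completion of the study". The Protocol Synopsis states: "Subjects who discontinue IP early for any reason will be asked to continue to return for all other study procedures". Protocol 6.2.2 says that a subject who cannot tolerate a dose "will continue to return for all other study procedures and measurements until the end of the study". Protocol 12.4 extends the data collection duty to all subjects, "including subjects not receiving protocol-required therapies". No expected retrieval rate is given.

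**The concern.** The trigger counts one thing and the method depends on another. Donors are taken within arm, so what matters is how many retrieved discontinuers each arm has. A pooled count can fail while evolocumab, where the off-treatment assumption matters most, has a reasonable donor pool. For example, 18 evolocumab and 6 placebo donors make 24, and the analysis is not run. The pooled count can also be met with few placebo donors.

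The trigger also works against need. For a given discontinuation rate, lower retrieval means more missing values and fewer donors, so the check is least likely to run when most data are missing.

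What would be lost is the planned data-based check on the zero-mean assumption. That assumption sets the off-treatment mean; the conditional analysis would estimate it.

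**Working it through.** **Inputs.** From SAP 3.2: 150 subjects (100 and 50), 20% discontinuing IP, effect 40 points, SD 20, two-sided 0.05. From SAP 10.5.1.2: trigger 25. Assumed, because the documents are silent: discontinuation and retrieval equal in both arms, subjects independent, retrieval r from 50% to 100%.

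**The plan's own figure.** With 80 and 40 subjects left after 20% loss, the noncentrality is 40 / [20 × √(1/80 + 1/40)] = 10.3 and power exceeds 0.999. With all 150 kept and the effect diluted to 0.8 × 40 = 32 points, it is 32 / [20 × √(1/100 + 1/50)] = 9.2, again above 0.999. The stated 99% is met with room to spare, so significance is not in question.

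**Chance that the analysis runs.** Expected discontinuers are 0.20 × 150 = 30 (20 evolocumab, 10 placebo). Reaching 25 needs 25/30 = 83% of them retrieved. P(run) = P(Binomial(150, d × r) ≥ 25), where d is the discontinuation rate:

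| Retrieval | d = 15% | d = 20% | d = 25% |
|---|---|---|---|
| 50% | 0.01% | 0.8% | 8% |
| 60% | 0.2% | 5.6% | 32% |
| 70% | 1.4% | 20% | 64% |
| 80% | 5.6% | 45% | 87% |
| 90% | 15% | 70% | 97% |
| 100% | 32% | 87% | 99% |

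An even chance needs r = 82% at d = 20% and r = 66% at d = 25%.

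**Skipped donor pools.** With independent Binomial(100, 0.2r) and Binomial(50, 0.2r), the chance that the total is below 25 while evolocumab has at least 10 donors is 54%, 72%, 71%, 52%, 29% and 13% for r = 50% to 100%.

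**Too few placebo donors when it runs.** Twenty-five donors split 2:1 give about 16.7 and 8.3. Given that the trigger is met, placebo has 5 or fewer donors in 7.4%, 6.8%, 6.0%, 5.0%, 3.9% and 2.7% of cases.

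**What is at stake.** Missing evolocumab discontinuers number 20(1 − r). If all of them kept the full 40-point effect, the zero-mean assumption would misplace the arm mean by 20(1 − r) × 40/100 = 4.0, 3.2, 2.4, 1.6, 0.8 and 0 points. If they kept half of it, the error would be 2.0, 1.6, 1.2, 0.8, 0.4 and 0 points. The standard error of the treatment difference is about 20 × √(1/100 + 1/50) = 3.5 points.

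The documents point to less retained effect than either case. Protocol 2.2.2 says that with 420 mg monthly dosing LDL-C is lowest at about 2 weeks, is already moving back by the end of the dosing interval, and that the reductions reverse after stopping. The last scheduled dose is at week 20, so an early stopper was last dosed, on schedule, at week 16 or before. That is at least 24 − 16 = 8 weeks, or two dosing intervals, before the endpoint.

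**Does counting by arm help?** Splitting the same total into minimums of 17 and 8 would run the analysis less often than now at 20% discontinuation: 0.3%, 2.2%, 9.2%, 24%, 45% and 65%. The gain comes only from a lower bar. Minimums of 10 and 5 would run with chance 31%, 57%, 77%, 89% and 95% at 50% to 90% retrieval.

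**What a lower bar costs.** Suppose values are drawn from a normal model fitted to n donors, with mean and variance both redrawn. The predictive variance is then (1 + 1/n)(n − 1)/(n − 3) times the donor variance:

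- n = 5: 1.2 × 4/2 = 2.4 times
- n = 8: 1.125 × 7/5 = 1.58 times

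Five donors among 20 evolocumab discontinuers leave 15 missing, and uncertainty in the donor mean adds (15/100) × 20/√5 = 1.34 points to the arm mean. With a minimum of 5 per arm and the zero-mean assumption as fallback, only evolocumab would qualify in 42%, 27%, 15%, 8%, 4% and 2% of trials. The two arms would then be imputed under different assumptions.

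**The case for a change.** The strongest case for a change is that the zero-mean analysis fixes by assumption what the second analysis would estimate, and that the estimate fits the adherence-free estimand better. Reversibility is stated without a full time course. Protocol 7.7.6 keeps lipid panels away from site staff until at least 12 weeks after the last dose, whereas a subject last dosed at week 16 is only 8 weeks out at week 24. The detail was added with FDA feedback as the rationale, yet it may seldom be used. Rewriting the rule would take one paragraph and no new data, and leaving the case below 25 open invites a choice after unblinding.

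Part of this stands. The mismatch between a pooled count and within-arm donors is real, the probabilities are right, and some residual effect at week 24 cannot be excluded. But the 12-week restriction is a blinding precaution and not evidence of persistence. The case below 25 is not truly open: the condition fails, the analysis is not run, and the zero-mean analysis is reported. SAP 9.3.1 calls for descriptive summaries of missing efficacy data, and SAP 9.4 allows further sensitivity analyses for potential bias in the primary endpoint, so a donor-based look at a smaller pool is not barred. A pooled count can also be checked before unblinding, which a count by arm cannot. As for the missing reason for 25, the FDA feedback is not among the documents, so its absence from the SAP does not show that none exists.

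**Conclusion.** No change is needed. The trigger is a rough stability threshold for a supplementary analysis. Under 2:1 allocation it serves as a workable proxy for the smaller arm: about 8 placebo donors are expected at 25, and 5 or fewer occur in under 8% of the trials that meet it. Its cost is that the analysis may often be skipped, with a chance of running between 0.8% and 87% at 20% discontinuation depending on retrieval.

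Skipping it loses little. Observed off-treatment values are in the primary model, the zero-mean imputation always runs, power exceeds 0.999, and the possible error in the evolocumab mean is bounded by 4.0 points at 50% retrieval and shrinks to nothing at full retrieval. A lower per-arm minimum would buy more frequent use at the price of noisier imputation and, in up to 42% of trials, different assumptions by arm. Reasonable statisticians would choose differently here. Reporting donors and missing values by arm is ordinary practice and would show a reader how much rests on the assumption.

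These figures assume equal discontinuation and retrieval in both arms, retrieval of 50% to 100%, and the planned SD of 20. What counts as a usable donor pool is not defined in the documents; the cut-offs of 5, 8 and 10 are illustrative.

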10.5.1.3 Subgroup Analyses of Primary Efficacy Endpoints

Subgroup analyses on the primary efficacy endpoints will be conducted using the subgroups specified in [Section 7.3](#). Treatment effect differences among subgroups, which represent subgroup by treatment interactions, will be estimated and tested based on statistics from the subgroup repeated measures models.

For subgroup analyses, the stratification factors from the eCRF will be used. Differences in stratum assignment between data collection via IVRS and eCRF will be tabulated.

10.5.2 Analyses of Secondary Efficacy Endpoints

The statistical model and testing of the secondary efficacy endpoints will be similar to the primary analysis of the primary endpoint.

Multiplicity adjustment procedures are defined in [Section 10.1](#)

10.5.3 Analyses of Tertiary Efficacy Endpoints

Analysis of the tertiary efficacy endpoints will be similar to the primary analysis of the primary endpoints. No multiplicity adjustment will be applied.

10.5.4 Analyses of Exploratory Endpoints

10.6 Safety Analyses

10.6.1 Adverse Events

The Medical Dictionary for Regulatory Activities (MedDRA) version **19.0** or later will be used to code all events categorized as adverse events (AE) to a system organ class and a preferred term. Severity of AEs will be graded using the CTCAE ([Appendix B](#)) and recorded on the eCRF. All adverse event tables will be summarized by actual treatment group. Treatment-emergent adverse events are events with an onset after the administration of the first dose of IP.

Subject Incidence of AEs will be summarized for all TEAEs, TE serious AEs, TEAE leading to withdrawal of investigational product and fatal TEAEs. Subject incidence of all treatment-emergent AEs, serious TEAEs, TEAEs leading to withdrawal of investigational product and fatal TEAE will be tabulated by system organ class, high level group term and preferred term.

Summaries of TE AEs occurring in at least 1% of the subjects by preferred term in any treatment arm will be provided in descending order of frequency.

Subject incidence of adverse events related to a device will be tabulated by preferred term in descending order of frequency by treatment group.

Subject incidence of adverse events associated with injectable protein therapies:

- Injection site reactions
- Hypersensitivity or allergic reactions
- potential neurocognitive events

will be summarized by category and preferred term.

Tanner stage will be summarized by treatment group and gender. A shift table for hsCRP will be provided, for levels at baseline to maximum post-baseline value (<1, 1-3, >3 mg/L), by treatment group. HbA1c, carotid intimal-medial thickness (cIMT) and steroid hormones will be summarized at each scheduled assessment by treatment group.

10.6.2 Laboratory Test Results

Descriptive statistics will be provided for actual values and changes from baseline in select laboratory parameters at each protocol-specified scheduled visit. Laboratory analytes are provided in the protocol Table 2. Lab shift tables using the CTCAE v4.03 or later grading will be used for analytes of interest, when applicable. The results will be based on the maximum (ie, worst) shift from baseline to the EOS. In addition, CK and liver function test (LFT) abnormalities will be assessed by the incidence overall and by visits of the following categories:

- CK > 5 x ULN
- CK > 10 x ULN
- ALT or AST \geq 3 x ULN
- ALT or AST \geq 5 x ULN
- Total bilirubin \geq 2 x ULN
- (ALT or AST \geq 3 x ULN) and Total bilirubin \geq 2 x ULN and Alkaline Phosphatase <2 x ULN

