6.5 Hepatotoxicity Stopping and Rechallenge Rules

Subjects with abnormal hepatic laboratory values (ie, alkaline phosphatase [ALP], aspartate aminotransferase [AST], alanine aminotransferase [ALT], total bilirubin [TBL]) and/or international normalized ratio [INR] and/or signs/symptoms of hepatitis (as described below) may meet the criteria for withholding or permanent discontinuation of Amgen investigational product or other protocol-required therapies as specified in the FDA Guidance for Industry Drug-Induced Liver Injury: Premarketing Clinical Evaluation, July 2009.

6.5.1 Criteria for Permanent Discontinuation of Amgen Investigational Product and Other Protocol-required Therapies Due to Potential Hepatotoxicity

Statin and investigational product should be discontinued permanently and the subject should be followed according to the recommendations in [Appendix A](#) (Additional Safety

Assessment Information) for possible drug-induced liver injury (DILI), if ALL of the criteria below are met:

- TBL > 2x ULN or INR > 1.5 (testing determined per [Appendix A](#))

AND

- AST or ALT > 3x ULN

AND

- no other cause for the combination of the above laboratory abnormalities is immediately apparent; important alternative causes for elevated AST/ALT and/or TBL values include, but are not limited to:
 - hepatobiliary tract disease
 - viral hepatitis (eg, hepatitis A/B/C/D/E, Epstein-Barr virus, cytomegalovirus, herpes simplex virus, varicella, toxoplasmosis, and parvovirus)
 - right sided heart failure, hypotension or any cause of hypoxia to the liver causing ischemia.
 - exposure to hepatotoxic agents/drugs or hepatotoxins, including herbal and dietary supplements, plants and mushrooms
 - heritable disorders causing impaired glucuronidation (eg, Gilbert's Syndrome, Crigler-Najjar syndrome) and drugs that inhibit bilirubin glucuronidation (eg, indinavir, atazanavir)
 - alpha-one antitrypsin deficiency
 - alcoholic hepatitis
 - autoimmune hepatitis
 - Wilson's disease and hemochromatosis
 - nonalcoholic fatty liver disease including steatohepatitis (NASH)
 - Non-hepatic causes (eg, rhabdomyolysis, hemolysis)

6.5.2 Criteria for Conditional Withholding of Amgen Investigational Product and Other Protocol-required Therapies Due to Potential Hepatotoxicity

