14. APPENDICES

Appendix A. Additional Safety Assessment Information

Adverse Event Grading Scale

Refer to the NCI Common Terminology Criteria for Adverse Events (CTCAE) Version 4.0 for adverse event grading and information. The CTCAE is available at the following link: http://ctep.cancer.gov/protocolDevelopment/electronic_applications\ctc.htm.

Pediatric Drug-induced Liver Injury Reporting & Additional Assessments

Reporting

Cases with

AST or ALT ≥ 3 x ULN and TBL > 2 x ULN or INR > 1.5

or

AST or ALT ≥ 3 x ULN with signs and symptoms consistent with hepatitis must be reported to Amgen as a serious adverse event within 24 hours of discovery or notification of the event (ie, before additional etiologic investigations have been concluded).

Cases with

AST or ALT > 3 x ULN (if baseline ALT or AST is ≤ 3 x ULN)

AST or ALT > 5 x ULN (if baseline ALT or AST is ≤ 5 x ULN)

are to be reported as adverse events.

The appropriate CRF (eg, Adverse Event CRF) that captures information necessary to facilitate the evaluation of treatment-emergent liver abnormalities is to be completed and sent to the Amgen.

Other events of hepatotoxicity and potential DILI are to be reported as serious adverse events if they meet the criteria for a serious adverse event defined in [Section 9.1.2](#).

Additional Clinical Assessments and Observation

All subjects in whom investigational medicinal product(s) or protocol-required therapies is/are withheld (either permanently or conditionally) due to potential DILI as specified in [Sections 6.5.1](#) and [Section 6.5.2](#) or who experience AST or ALT elevations > 3 x ULN (if baseline ALT or AST is ≤ 3 x ULN) or who experience AST or ALT > 5 x ULN (if baseline

ALT or AST is $\leq 5 \times$ ULN) are to undergo a period of “close observation” until abnormalities return to normal or to the subject’s baseline levels.

The following evaluations are to be performed during this period:

1. Repeat liver tests AST, ALT, ALP, bilirubin (total and direct), and INR as clinically necessary until laboratory abnormalities improve .
2. Obtain pediatric gastroenterologist or pediatric hepatologist consult.

The diagnostic approach (including blood tests) to investigate alternative causes for abnormal liver tests is to be determined in consultation with a pediatric gastroenterologist or hepatologist.

The “close observation” is to continue until all laboratory abnormalities return to baseline or normalize and subject’s clinical condition improves.

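### The SAP's only combined liver row leaves out subjects with ALP at or above 2x ULN, although the protocol's liver stopping and SAE criteria have no ALP condition

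*SAP*

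**What the plan says.** SAP 10.6.2 states that CK and liver-test "abnormalities will be assessed by the incidence overall and by visits of the following categories". The list has two CK rows, three single-test liver rows (ALT or AST at least 3x ULN, ALT or AST at least 5x ULN, total bilirubin at least 2x ULN) and one combined liver row. The combined row requires ALT or AST at least 3x ULN together with bilirubin at least "2 x ULN and Alkaline Phosphatase <2 x ULN". No combined row without the ALP limit is listed.

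The protocol uses a joint elevation in two places:

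- **Section 6.5.1, permanent discontinuation.** All of the following are needed: "TBL > 2x ULN or INR > 1.5"; "AST or ALT > 3x ULN"; and a judgement that "no other cause for the combination of the above laboratory abnormalities is immediately apparent".
- **Appendix A, liver reporting.** Cases with "AST or ALT ≥ 3 x ULN and TBL > 2 x ULN or INR > 1.5" "must be reported to Amgen as a serious adverse event within 24 hours of discovery or notification of the event".

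Neither rule mentions ALP. The only ALP threshold in the protocol's liver rules is in 6.5.2, where ALP above 8x ULN is a separate trigger for conditional withholding.

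**The concern.** Transaminases and bilirubin raised together in one subject is the laboratory picture that the protocol singles out for permanent discontinuation and expedited reporting. A reader of the liver table will look at the combined row to learn whether this happened and in which arm. Because of the ALP limit, that row can show zero when a subject has met the protocol's own definition.

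The single-test rows do not repair this. A count of 1 for ALT or AST and a count of 1 for bilirubin, even at the same visit, could be one subject or two. The adverse-event tables in SAP 10.6.1 are arranged by system organ class, high level group term and preferred term. The grouped categories there are injection-site, hypersensitivity and neurocognitive events, with no hepatic grouping. The joint elevation is therefore not shown as a count by arm anywhere else in the SAP.

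Only a descriptive safety summary is at stake. No hypothesis test, efficacy result or clinical rule is involved.

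**Working it through.** The plan gives no figure to reproduce here. The check writes each rule as a logical condition, with ALT, AST, total bilirubin (TBL) and ALP in multiples of ULN, and applies the rules to test profiles.

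**Rules**

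- Protocol 6.5.1: (TBL > 2 or INR > 1.5) and (AST or ALT > 3) and no other cause apparent.
- Protocol Appendix A, SAE: (AST or ALT ≥ 3) and (TBL > 2 or INR > 1.5). The printed line has no brackets; this reading treats INR as an alternative to bilirubin, as in 6.5.1.
- SAP 10.6.2, combined row: (ALT or AST ≥ 3) and TBL ≥ 2 and ALP < 2.

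**Results, taking no other cause as apparent**

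| ALT | TBL | INR | ALP | 6.5.1 | App. A SAE | SAP combined | SAP ALT/AST ≥ 3x | SAP TBL ≥ 2x |
|---|---|---|---|---|---|---|---|---|
| 4 | 2.5 | 1.0 | 1.0 | yes | yes | yes | yes | yes |
| 4 | 2.5 | 1.0 | 1.99 | yes | yes | yes | yes | yes |
| 4 | 2.5 | 1.0 | 2.0 | yes | yes | **no** | yes | yes |
| 4 | 2.5 | 1.0 | 3.0 | yes | yes | **no** | yes | yes |
| 4 | 2.5 | 1.0 | 9.0 | yes | yes | **no** | yes | yes |
| 4 | 1.0 | 1.8 | 1.0 | yes | yes | **no** | yes | no |
| 4 | 1.0 | 1.8 | 3.0 | yes | yes | **no** | yes | no |

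Three things follow.

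1. For the bilirubin route, the combined row loses a case exactly when ALP is at or above 2x ULN. ALP between 1x and 2x ULN excludes nobody.
2. If q is the share of bilirubin-route cases with ALP at or above 2x ULN, the combined row misses the fraction q. The documents give nothing from which to estimate q, so 0 ≤ q ≤ 1.
3. The INR route never enters the combined row, whatever the ALP. Removing the ALP limit alone would not change that.

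**Scale of one case.** Protocol 10.2 plans 100 subjects on evolocumab. With 0/100 the exact 95% upper limit is 1 − 0.025^(1/100) = 3.6%. With 1/100 the exact interval is 0.03% to 5.4%. This shows what one omitted count does to a row of this size; it does not predict that a case will occur.

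**After the change.** With the condition (ALT or AST ≥ 3) and TBL > 2 and no ALP limit, the first profile is counted at all five ALP values. The INR profile is still not counted and needs a separate listing.

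**The case against.** The strongest reply is that very little is lost. A subject who qualifies through bilirubin enters the ALT/AST row and the bilirubin row at any ALP. Appendix A makes the case an SAE, and where 6.5.1 is met the investigational product stops permanently. A treatment-emergent case should therefore also appear in the serious-event and withdrawal tables of SAP 10.6.1. Protocol 10.5.5 also allows subject-level data in place of adverse-event tables when incidence is low. All of this stands. A reader might infer that such a subject goes uncounted altogether, or that the whole liver table would read zero; the documents do not support that. One row is affected, and it is the row that shows the joint elevation.

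A second reply is that a laboratory row need not copy a stopping rule. Section 6.5.1 also requires that no other cause be apparent, and hepatobiliary disease heads its list of alternatives. That is a clinical judgement that a table cannot apply. This also stands against 6.5.1, but not against Appendix A, whose SAE rule is purely numerical on this route and applies before the cause has been investigated.

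A third reply concerns INR. Table 1 does not schedule it, Table 2 lists it only as directed by Appendix A, and SAP Appendix A has no analysis window for it. INR would be known mainly for subjects already under close observation, so building it into an incidence row would mix tested and untested subjects. This stands, and it is why the INR route belongs in a listing.

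Finally, a reader might infer that ALP at this level is common at ages 10 to 17 because of growth, so that many cases would drop out. The documents give no frequency of ALP at or above 2x ULN and do not say whether the ULN is adjusted for age and sex. That inference, and any numerical range for the loss, has to be left aside.

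**Conclusion.** The point holds in a narrow form. The SAP's one combined liver row carries an ALP condition that neither the protocol's stopping rule nor its SAE rule has, so a subject who meets those rules with ALP at or above 2x ULN is left out of that row. The other tables show parts of the case but not the joint elevation by arm.

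The size cannot be stated beyond its bounds: the missed share of bilirubin-route cases lies between 0 and 1, and with about 150 subjects few or no cases are expected. The conclusion rests on comparing the definitions and needs no assumption about how often ALP is raised. It does assume that Appendix A is read with INR as an alternative to bilirubin. Priority: minor.

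**What to change.** In SAP 10.6.2, add a row for ALT or AST at least 3x ULN with total bilirubin above 2x ULN, regardless of ALP. This follows the bilirubin route of the Appendix A SAE rule. Keep the ALP-restricted row beneath it as a subset. For the nesting to be exact, both rows need the same bilirubin sign: the SAP row now includes a value of exactly 2x ULN, and Appendix A does not.

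List separately the subjects who meet the transaminase threshold with INR above 1.5, where INR was measured, and note that INR was not scheduled for all subjects.

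The cost is one table row and a short listing. ALT, AST, bilirubin and ALP are all in the chemistry panel of protocol Table 2, so no new data are needed. The broader row may include cholestatic or other non-drug cases, which would need a narrative. The change concerns reporting only and leaves the protocol's clinical rules untouched.
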